#### **8.4.3. Severity of Event**

Adverse events will be graded for severity according to the Common Terminology Criteria for Adverse Events (CTCAE) version 5.0

The following categories and definitions of intensity as determined by a physician must be used:

- Mild (Grade 1): Awareness of event but easily tolerated.
- Moderate (Grade 2): Discomfort enough to cause some interference with usual activity.
- Severe (Grade 3): Inability to carry out usual activity.
- Very Severe (Grade 4): Debilitating; significantly incapacitates subject despite symptomatic therapy.

#### **8.4.4. Intervention**

Any intervention implemented to treat the adverse event must be documented for all adverse events.

#### **8.4.5. Non-serious Adverse Event**

Non-serious Adverse Events (AE) are to be provided to BMS in aggregate via interim or final study reports as specified in the agreement or, if a regulatory requirement [eg, IND US trial] as part of an annual reporting requirement.

Non-serious AE information must also be collected from the start of a placebo lead-in period or other observational period intended to establish a baseline status for the subjects.

A ***non-serious adverse event*** is an AE not classified as serious.

#### **Non-serious Adverse Event Collection and Reporting**

The collection of non-serious AE information must begin at initiation of study drug. All non-serious adverse events (not only those deemed to be treatment-related) must be collected continuously during the treatment period and for a minimum of 30 days following the last dose of study treatment.

Non-serious AEs must be followed to resolution or stabilization, or reported as SAEs if they become serious. Follow-up is also required for non-serious AEs that cause interruption or discontinuation of study drug and for those present at the end of study treatment as appropriate.

## **8.5. Safety Reporting**

### **8.5.1. Reporting to the IRB**

#### **8.5.1.1. Unanticipated Problems**

All incidents or events that meet criteria for unanticipated problems (UAPs) require the creation and completion of an unanticipated problem report form.

UAPs that pose risk to participants or others, and that are not AEs, will be submitted to the IRB within 5 working days of the investigator becoming aware of the event.

UAPs that do not pose risk to participants or others will be submitted to the IRB at the next continuing review.

##### **8.5.1.1.1**

#### **Sub-Site Unanticipated Problems Reporting**

Unanticipated problems (UAPs) occurring at the sub-site are to be reported to the sub-site IRB per institutional guidelines.

UAPs occurring at the sub-site must also be reporting to Thomas Jefferson University using the Unanticipated Problems Form (see Appendix 2). The TJU Study Site Contact will submit UAPs occurring at the sub-site to the TJU IRB.

#### **8.5.1.2. Adverse Events**

Grade 1 AEs will be reported to the IRB at continuing review.

Grade 2 AEs will be reported to the IRB at the time of continuing review.

#### **8.5.1.3. Serious Adverse Events**

SAEs will be reported to the IRB.

Grade 3-4 AEs that are unexpected and deemed to be at least possibly related to the study will be reported to the IRB within 2 working days of knowledge of the event.

Grade 3-4 AEs that are deemed unrelated to the study will be reported to the IRB within 5 working days.

Grade 5 AEs will be reported to the IRB within one working day of knowledge of the event.

All SAEs will be submitted to the IRB at continuing review, including those that were reported previously.

SAEs occurring at the sub-site are to be reported to the sub-site IRB per institutional guidelines. Section 8.5.1.4 provides information on reporting SAEs to TJU.

#### **8.5.1.4 Sub-Site SAE Reporting**

All SAEs occurring at the sub-site must be reported to the TJU Study Site Contact within 24 hours of notification. This initial notification can take place via email or phone, followed by the submission of a formal report.

SAEs must be reported to TJU using the FDA Medwatch 3500A, and must comprise a full written summary, detailing relevant aspects of the adverse events in questions, including grading and attribution to study drug. Where applicable, information from relevant hospital case records and autopsy reports must be included.

SAE Reports must be signed by the sub-site PI, and then emailed to the Thomas Jefferson University Study Site Contact within 24 hours.

The TJU coordinator will notify the TJU PI and obtain the TJU PI signature, and report these events to the TJU Medical Monitor/IRB appropriately (within 5 working days if it deems an amendment, or in a spreadsheet at the time of annual review if no amendment is necessary).

Additional follow-up SAE reports must be submitted when available.

All reportable Adverse Events (AEs) must be reported to the TJU Research Coordinator within 48 hours using the FDA MedWatch 3500 form.

A reportable AE is any adverse event NOT identified in the IB or consent form as a risk.

Any non-reportable AE must be kept by the sub-site on an ongoing tracking log to be reviewed by TJU quarterly.

Unanticipated problems (UAPs) that pose risk to subjects or others, and that are not AEs/SAEs should be reported to TJU within 5 working days using form Unanticipated Problems Form (see Appendix 2) and must be emailed to the TJU Study Site Contact within 5 business days.

### **8.5.2 Reporting to SKCC DSMC**

All AEs and SAEs, safety and toxicity data, and any corrective actions will be submitted to the DSMC per the frequency described in the SKCC DSMP. The report to the SKCC DSMC will also include any unanticipated problems that in the opinion of the PI must be reported to the DSMC.

The sub-site is required to provide copies of any Unanticipated Problems, protocol deviations, and AE logs to the TJU Study Site Contact for submission to the DSMC.

For expedited reporting requirements, see table below:

DSMC AE/SAE Reporting Requirements

	Grade 1	Grade 2		Grade 3				Grades 4 and 5
	Unexpected and Expected	Unexpected	Expected	Unexpected		Expected		Unexpected and Expected
				With Hospitalization	Without Hospitalization	With Hospitalization	Without Hospitalization	
Unrelated Unlikely	Reviewed at Quarterly DSMC Meeting and IRB Annual Review	Reviewed at Quarterly DSMC Meeting and IRB Annual Review	Reviewed at Quarterly DSMC Meeting and IRB Annual Review	5 Working Days	Reviewed at Quarterly DSMC Meeting and IRB Annual Review	5 Working Days	Reviewed at Quarterly DSMC Meeting and IRB Annual Review	Phase I - 48 Hours (Death: 24 Hours) Phase II - 5 working days
Possible Probably Definite	Reviewed at Quarterly DSMC Meeting and IRB Annual Review	Reviewed at Quarterly DSMC Meeting and IRB Annual Review	Reviewed at Quarterly DSMC Meeting and IRB Annual Review	48 Hours (Death: 24 Hours)	Phase I - 48 Hours Phase II - 5 working days	48 Hours (Death: 24 Hours)	Reviewed at Quarterly DSMC Meeting and IRB Annual Review	Phase I and Phase II - 48 Hours (Death: 24 Hours)

### 8.5.3. SKCC Reporting SAEs to BMS

All Serious Adverse Events (SAEs) that occur following the subject's initiation of study treatment, unless AE/SAE is caused by a study specific screening procedure, through 30\* days of discontinuation of dosing must be reported to BMS Worldwide Safety, whether related or not related to study drug. If applicable, SAEs must be collected that relate to any later protocol-specified procedure (eg, a follow-up skin biopsy).

Following the subject's initiation of treatment, unless AE/SAE is caused by a study specific screening procedure, all SAEs, whether related or not related to study drug, are collected, including those thought to be associated with protocol-specified procedures. The investigator must report any SAE occurring after these aforementioned time periods, which is believed to be related to study drug or protocol-specified procedure.

An SAE report must be completed for any event where doubt exists regarding its seriousness;

If the investigator believes that an SAE is not related to study drug, but is potentially related to the conditions of the study (such as withdrawal of previous therapy or a complication of a study procedure), the relationship must be specified in the narrative section of the SAE Report Form.

If the BMS safety address is not included in the protocol document (eg, multicenter studies where events are reported centrally), the procedure for safety reporting must be reviewed/approved by the BMS Protocol Manager. Procedures for such reporting must be reviewed and approved by BMS prior to study activation.

An appropriate SAE form (e.g. ex-US = CIOMS form or USA = Medwatch form) must be used to report SAEs to BMS. The BMS protocol ID number must be included on whatever form is submitted by the Sponsor/Investigator.

- The CIOMS form is available at: <http://www.cioms.ch/index.php/cioms-form-i>
- The MedWatch form is available at:  
<https://www.fda.gov/downloads/AboutFDA/ReportsManualsForms/Forms/UCM048334.pdf>

The sponsor will reconcile the clinical database SAE cases (case level only) transmitted to BMS Global Pharmacovigilance ([[contact]](mailto:[contact])). Frequency of reconciliation must be every 3 months and prior to the database lock or final data summary. GMS GPV&E will email, upon request from the Investigator, the GPV&E reconciliation report. Requests for reconciliation must be sent to [[contact]](mailto:[contact]). The data elements listed on the GPV&E reconciliation report will be used for case identification purposes. If the Investigator determines a case was not transmitted to BMS GPV&E, the case must be sent immediately to BMS.

In accordance with local regulations, BMS will notify investigators of all reported SAEs that are suspected (related to the investigational product) and unexpected (ie, not previously described in the IB). An event meeting these criteria is termed a Suspected, Unexpected Serious Adverse Reaction (SUSAR). Investigator notification of these events will be in the form of a SUSAR Report.

- Other important findings which may be reported by BMS as an Expedited Safety Report (ESR)

include: increased frequency of a clinically significant expected SAE, an SAE considered associated with study procedures that could modify the conduct of the study, lack of efficacy that poses significant hazard to study subjects, clinically significant safety finding from a nonclinical (eg, animal) study, important safety recommendations from a study data monitoring committee, or sponsor decision to end or temporarily halt a clinical study for safety reasons.

- Upon receiving an ESR from BMS, the investigator must review and retain the ESR with the IB. Where required by local regulations or when there is a central IRB/IEC for the study, the sponsor will submit the ESR to the appropriate IRB/IEC. The investigator and IRB/IEC will determine if the informed consent requires revision. The investigator must also comply with the IRB/IEC procedures for reporting any other safety information.
- In addition to the Sponsor Investigator's responsibility to report events to their local HA, suspected serious adverse reactions (whether expected or unexpected) shall be reported by BMS to the relevant competent health authorities in all concerned countries according to local regulations (either as expedited and/or in aggregate reports).

SAEs, whether related or not related to study drug, and pregnancies must be reported to BMS within 24 hours. SAEs must be recorded on either CIOMS or MedWatch form & pregnancies must be reported on a Pregnancy Surveillance Form or can be submitted on the aforementioned SAE form to BMS.

**SAE Email Address:** [contact]

**SAE [contact]

If only limited information is initially available, follow-up reports are required. (Note: Follow-up SAE reports must include the same investigator term(s) initially reported.)

If an ongoing SAE changes in its intensity or relationship to study drug or if new information becomes available, a follow-up SAE report must be sent within 24 hours to BMS (or designee) using the same procedure used for transmitting the initial SAE report.

All SAEs must be followed to resolution or stabilization.

#### **8.5.4 SKCC Reporting to the FDA**

For studies conducted under an Investigator IND in the US, any event that is both serious and unexpected must be reported to the Food and Drug Administration (FDA) as soon as possible and no later than 7 days (for a death or life-threatening event) or 15 days (for all other SAEs) after the investigator's or institution's initial receipt of the information. BMS will be provided with a simultaneous copy of all adverse events filed with the FDA.

SAEs must be reported on MedWatch Form 3500A, which can be accessed at:

<http://www.accessdata.fda.gov/scripts/medwatch/>.

MedWatch SAE forms must be sent to the FDA at:

**Global Pharmacovigilance & Epidemiology**

**Bristol-Myers Squibb Company**

**[contact]**

**Email: [[contact]](mailto:[contact])**

- An SAE report must be completed for any event where doubt exists regarding its seriousness.
- For studies with long-term follow-up periods in which safety data are being reported, include the timing of SAE collection in the protocol.
- If the investigator believes that an SAE is not related to study drug, but is potentially related to the conditions of the study (such as withdrawal of previous therapy or a complication of a study procedure), the relationship must be specified in the narrative section of the SAE Report Form.
- If only limited information is initially available, follow-up reports are required. (Note: Follow-up SAE reports must include the same investigator term(s) initially reported.)
- If an ongoing SAE changes in its intensity or relationship to study drug or if new information becomes available, a follow-up SAE report must be sent within 24 hours to BMS using the same procedure used for transmitting the initial SAE report. All SAEs must be followed to resolution or stabilization. All SAEs must be followed to resolution or stabilization.

For any fatal or life-threatening adverse event that is unexpected and assessed by the investigator as possibly related to the use of nivolumab, the sub-site must submit a completed FDA Medwatch 3500A Form and email form to the TJU study site contact for submission to the FDA and BMS. The initial communication may take place via telephone but must be followed up with the completed form within 24 hours of first learning of the event.

## **8.6 Study Oversight**

In addition to the PI's responsibility for oversight, study oversight will be under the direction of the SKCC's Data and Safety Monitoring Committee (DSMC). The SKCC DSMC operates in compliance with a Data and Safety Monitoring Plan (DSMP) that is approved by the NCI.

## **8.7 Clinical Site Monitoring and Auditing**

Clinical site monitoring and auditing is conducted to ensure that the rights of human participants are protected, that the study is implemented in accordance with the protocol and/or other operating procedures, and that the quality and integrity of study data and data collection methods are maintained. Monitoring and auditing for this study will be performed in accordance with the SKCC's Data and Safety Monitoring Plan (DSMP) developed by the SKCC Data and Safety Monitoring Committee (DSMC). The DSMP specifies the frequency of monitoring, monitoring procedures, the level of clinical site monitoring activities (e.g., the percentage of participant data to be reviewed), and the distribution of monitoring reports. Some monitoring activities may be performed remotely, while others will take place at the study site(s). Appropriate staff will conduct monitoring activities and provide reports of the findings and associated action items in accordance with the details described in the SKCC DSMP.

## **9. STATISTICAL CONSIDERATIONS**

### **9.1. Analysis Plan**

#### **9.1.1. Baseline Characteristics**

Baseline descriptive statistics on all evaluable patients will be provided on demographic variables (age, sex, and race/ethnicity), performance status, laboratory parameters, the treatment regimens that were previously used, and disease characteristics.

#### **9.1.2. Survival and Recurrence-free Survival**

Patients' survival times will be measured from the initial date of treatment to the recorded date of death. Recurrence-free survival (RFS) will be measured from the initial date of treatment to the date of documented recurrence. Distant Metastases-free survival (DMFS) is defined as the time from definitive surgery to the date of diagnosis of metastatic disease.

Overall survival and recurrence-free survival (RFS) will be estimated by the Kaplan-Meier method. The corresponding median survival times (with 90% confidence limits) will be determined, as will the cumulative percentage of patients remaining progression-free / alive at selected time points after initial treatment (e.g., 6, 12, and 18 months).

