### **2.2. Primary Endpoint**

- The primary end point is recurrence-free survival at 24 months. Recurrence-free survival time is defined as the number of days from study registration until documented progression or death without documentation of disease progression.

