### **9.3. Sample Size Considerations**

Based upon recent retrospective analyses, the 24 month recurrence free survival rate for our patient population is 70%. To demonstrate a 50% improvement in the 24 month recurrence free survival rate (0.70 vs 0.85), with power of 0.90, alpha 0.05 using one arm non-parametric survival (one-sided) test, we will require enrollment of 63 evaluable patients. To account for potential loss to follow up of 15%, our target number of enrolled subjects is 73. We will require 24 months of follow-up for all patients for evaluation of the primary endpoint.

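### The primary endpoint, RFS, has two incompatible definitions: Section 2.2 counts deaths and starts at registration, Section 9.1.2 counts only documented recurrence and starts at first treatment, and nothing says which governs

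*Combined protocol and SAP*

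**What the plan says.** Section 2.2 (Primary Endpoint) counts RFS time in days "from study registration until documented progression or death without documentation of disease progression". Death without prior progression is therefore an event, and the clock starts at registration.

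Section 9.1.2 (Survival and Recurrence-free Survival) gives a different rule: "Recurrence-free survival (RFS) will be measured from the initial date of treatment to the date of documented recurrence". Death is not named as an event, and the clock starts at first treatment. The same section adds: "Overall survival and recurrence-free survival (RFS) will be estimated by the Kaplan-Meier method". It gives no rule for a patient who dies without documented recurrence.

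Section 9.3 (Sample Size Considerations) sets 0.70 against 0.85 at 24 months "with power of 0.90, alpha 0.05 using one arm non-parametric survival (one-sided) test" and arrives at 63 evaluable patients. It does not define RFS. Section 1.2.1 derives the 70% benchmark from retrospective recurrence rates of about 32% (stage IIB) and 46% (stage IIC), without saying how deaths were treated in those data.

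**The concern.** This is the only endpoint with a stated hypothesis, power and alpha, and it is compared with a fixed number. There is no control arm in which a shift in definition would cancel out. An analyst who follows Section 9.1.2 would not compute the endpoint promised in Section 2.2.

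The event set matters most. If deaths without documented recurrence are censored, Kaplan-Meier treats those patients as still able to remain recurrence-free. Such deaths can be foreseen: Section 5.6 says that fatal lung inflammation has occurred in rare cases with nivolumab. A death of that kind would not count against treatment in the primary analysis. Leaving both definitions in place also allows the choice between them to be made after the data are seen.

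**Working it through.** **1. The plan's own figure.** Inputs from Section 9.3: p0 = 0.70, p1 = 0.85, one-sided alpha 0.05 (z = 1.645), power 0.90 (z = 1.282). With the arcsine square-root transformation and no censoring before 24 months:

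N = (1.645 + 1.282)² / [4 (asin√0.85 − asin√0.70)²] = 8.564 / [4 × (1.1731 − 0.9912)²] = 64.7, so 65.

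The stated 63 is within two patients of this, and normal-approximation power at 63 is 88.9%. The calculation uses only p0, p1, alpha and power, so choosing one event definition does not alter N unless p0 or p1 is restated.

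**2. The definitions side by side.**

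| | Section 2.2 | Section 9.1.2 |
|---|---|---|
| Origin | registration | first treatment |
| Recurrence or progression | event | event |
| Death without it | event | not named; no censoring rule |

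**3. Effect of the event set.** Let d be the probability of death without documented recurrence by 24 months, net of recurrence. The documents give no value; 1% to 4% is assumed. With independent hazards, composite RFS = (recurrence-only curve) × (1 − d), so the recurrence-only estimate is 0.70 / (1 − d) when composite RFS is 0.70. With constant hazards, the expected number of such deaths among 63 is [ln(1 − d) / ln 0.70] × 0.30 × 63.

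| d | Expected deaths among 63 | Recurrence-only estimate | Excess (points) |
|---|---|---|---|
| 0 | 0 | 0.700 | 0 |
| 1% | 0.53 | 0.707 | 0.7 |
| 2% | 1.07 | 0.714 | 1.4 |
| 3% | 1.61 | 0.722 | 2.2 |
| 4% | 2.16 | 0.729 | 2.9 |

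The size is assumed, but the direction is not: censoring these deaths instead of counting them cannot lower the Kaplan-Meier curve.

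**4. Effect on the test, in two cases.** The plan states no cut-off. For illustration, take an exact binomial rule with 63 fully observed patients. The smallest count with one-sided error at or below 0.05 at p = 0.70 is 51: P(X ≥ 51) = 0.035, while P(X ≥ 50) = 0.065.

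- *The 70% counted deaths, and 9.1.2 is used.* The success probability under the null becomes 0.70 / (1 − d). P(X ≥ 51) is 4.6%, 5.8%, 7.5% and 9.5% for d = 1%, 2%, 3% and 4%. A normal approximation at nominal 5% gives 6.3%, 7.8% and 9.7% for d = 1%, 2% and 3%.
- *The 70% is recurrence-only, and 2.2 is used.* The success probability becomes 0.70 × (1 − d), or 0.693 to 0.672 for d = 1% to 4%. P(X ≥ 51) falls from 3.5% to between 2.7% and 1.2%.

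**5. Effect of the origin alone.** Let H(t) = −ln(0.70) × (t/24)^k, with a lag L of 0.25 to 1 month between registration and first dose (assumed; no interval is documented). Measured from first dose, 24-month RFS is exp{−[H(24 + L) − H(L)]}.

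- Constant hazard (k = 1): 0.700, no change.
- Falling hazard (k = 0.8): 0.704 to 0.711.
- Rising hazard (k = 1.3): 0.697 to 0.691.

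The shift is about one point at most over this range, in either direction.

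**The case against.** The strongest reply is that Section 2.2 is the only definition under the primary-endpoint heading and that it plainly includes death, so 9.1.2 may be loose drafting. Section 9.1.2 never says that deaths are censored, and it also speaks of patients "remaining progression-free / alive at selected time points after initial treatment (e.g., 6, 12, and 18 months". The first part carries weight: censoring is the natural Kaplan-Meier reading of 9.1.2, not a stated rule. The quoted phrase does not help, because it covers the RFS and overall-survival summaries together. Nothing states that 2.2 prevails, so the conflict stands.

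A reader might infer three stronger things that the documents do not support.

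- *That the test's false-positive rate is inflated.* This needs a benchmark that counted deaths. Section 1.2.1 speaks only of recurrence rates. If those excluded deaths, 9.1.2 is the like-for-like comparison, and testing the 2.2 endpoint against 70% is conservative.
- *That the later time origin adds to the overstatement.* Its effect has no fixed direction, and no registration-to-treatment interval is given. Section 6.1 gives only a 28-day screening window.
- *That treatment-related deaths disappear from the trial.* They remain in overall survival, in serious adverse event reporting (Sections 8.2.3 and 8.5.1.3) and in the death information sought under Section 7.3. They would be missing only from RFS.

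The 51-of-63 rule is also open to objection. It is not in the plan, and it treats censored patients as fully observed. The figures from it are illustrative only.

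**Conclusion.** The contradiction is real and concerns the only powered endpoint. If Section 9.1.2 is followed and deaths without documented recurrence are censored, the 24-month estimate is at or above the Section 2.2 endpoint. The excess is about 0.7 to 2.9 points at a true RFS of 70%, for an assumed 1% to 4% risk of such death; with no such deaths before 24 months it is zero.

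The consequence for the test is conditional. If the 70% counted deaths, one-sided type I error rises, illustratively from 3.5% to between 4.6% and 9.5%. If it did not, the mismatch lies between the benchmark and Section 2.2. Either way, one definition and a matching benchmark are needed before analysis, because one or two deaths among 63 could decide the result: under the illustrative rule, 51 successes reject 70% and 50 do not.

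The difference in origin is a separate and minor inconsistency. It still needs an answer, since 9.1.2 gives no time zero for a patient who is registered but never treated.

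**What to change.** - Amend Section 9.1.2 to match Section 2.2: RFS is the time to first local, regional or distant recurrence or death from any cause. Use the word recurrence consistently in both sections.
- State one origin in both sections. Keeping registration, as in 2.2, is the smaller change and retains patients registered but never treated; first dose can be a sensitivity analysis. Making first dose the primary origin would be a preference, not a correction.
- State that event-free patients are censored at their last disease assessment.
- Confirm from the retrospective data whether the 70% counted deaths, and restate it if it did not.

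The cost is a wording amendment plus a check of the benchmark's source. The estimate may be slightly less favourable to treatment. The 63 patients stand unless the benchmark is restated, in which case Section 9.3 must be recalculated.
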